14.3. Changes to Final Protocol

All protocol amendments must be submitted to the ethics committee and regulatory authorities if required by local law. Protocol modifications that affect participant safety, the scope of the investigation, or the scientific quality of the study must be approved by the ethics committee before implementation of such modifications to the conduct of the study. If required by local law, such modifications must also be approved by the appropriate regulatory agency prior to implementation.

However, the Sponsor may, at any time, amend this protocol to eliminate an apparent immediate hazard to a participant. In this case, the appropriate regulatory authorities will be notified subsequent to the modification.

In the event of a protocol modification, the ICF may require similar modifications (see Section 14.4).

14.4. Informed Consent

Prior to performing any study-related activities under this protocol, including screening tests and assessments, informed consent with the approved ICF must be obtained.

The background of the proposed study, the procedures, the benefits and risks of the study, and that study participation is voluntary for the participant must be explained to the participant and/or the participant's legally authorized representative. The participant and/or the participant's legally authorized representative must be given sufficient time to consider whether to participate in the study.

A copy of the signed and dated ICF must be given to the participant and/or the participant's legally authorized representative. The original signed and dated ICF will be retained with the study records. Local regulations must be complied with in respect to the final disposition of the original and copies of the signed and dated ICFs.

Confirmation of informed consent must also be documented in the participant's medical record.

When additional information that may affect participants' willingness to continue in the study becomes available, the Investigators will be notified in a timely manner, according to all local and applicable law. An updated ICF may be required.

The participant's informants/caregivers must also provide written informed consent to participate in the study. The original forms will be managed and archived in the same manner as the participants' ICFs, as described in Section 14.4.

14.5. Participant Data Protection

Prior to any testing under this protocol, including screening tests and assessments, candidates must also provide all authorizations required by applicable national and local privacy regulations (e.g., Protected Health Information authorization in North America).

During the study, participants' race and ethnicity will be collected (unless the collection is not permitted by applicable law or not approved by the governing ethics committee). These data will be used in the analysis of the safety and/or PK profile of the study treatment. It is unknown whether the effects of the study treatment are influenced by race or ethnicity.

Study reports will be used for research purposes only. The participant will not be identified by name in CRFs, study-related forms, study reports, or any related publications. The Sponsor, its partners and designees, ethics committees, and various government health agencies may inspect the records of this study. Every effort will be made to keep the participant's personal medical data confidential.

14.6. Compensation for Injury

The Sponsor maintains appropriate insurance coverage for clinical studies and will follow applicable local compensation laws.

14.7. Conflict of Interest

The Investigators should address any potential conflicts of interest (e.g., financial interest in the Sponsor or with the participant before the participant makes a decision to participate in the study.

14.8. Study Report Signatory

The Sponsor will designate one or more of the participating Investigators as a signatory for the study report. This determination will be made by several factors, including but not limited to, the Investigator's experience and reputation in the studied indication; the Investigator's contribution to the study in terms of design, management, and/or participant enrollment; or by other factors determined to be relevant by the Sponsor.

14.9. Registration of Study and Disclosure of Study Results

The Sponsor will register the study and post study results regardless of outcome on a publicly accessible website in accordance with the applicable laws and regulations.

The Sponsor also will notify, when required, the regulatory authorities and ethics committees about the completion or termination of this study and send a copy of the study synopsis in accordance with necessary timelines.

14.10. Retention of Study Data

The minimum retention time for study records will meet the strictest standard applicable to that site, as dictated by any institutional requirements or local, national, or regional laws or regulations. Prior to proceeding with destruction of records, the Investigator must notify the Sponsor in writing and receive written authorization from the Sponsor to destroy study records. In addition, the Investigator must notify the Sponsor of any changes in the archival arrangements including but not limited to archival at an offsite facility or transfer of ownership if the Investigator leaves the site.

15. KEY ROLES AND STUDY GOVERNANCE COMMITTEES

15.1. Vendors

The Sponsor will ensure oversight of any study-related duties and functions carried out on its behalf and will specify in writing all duties and functions that are transferred.

15.1.1. Contract Research Organization

A CRO will be responsible for administrative aspects of the study including but not limited to study initiation, management of SAE reports, monitoring, and data management.

15.1.2. Interactive Response Technology

IRT will be used in this study. Before participants are screened or enrolled, the IRT vendor will provide each study site with the necessary training, a user manual, and access rights to the system.

15.1.3. Electronic Data Capture

Participant information will be captured and managed by study sites on electronic CRFs by a web-based electronic data capture tool configured by Sponsor and hosted by Metadata.

15.1.4. Digital Clinical Outcomes Data Capture

Participant information, including and ventilation diary logs, will be captured electronically to assess clinical outcomes.

15.1.5. Central Laboratories for Laboratory Assessments

A central laboratory has been selected by the Sponsor to analyze all hematology, coagulation testing, blood chemistry, and urine samples collected for this study, except for urine pregnancy tests and CSF, which will be analyzed by a local laboratory; repeat coagulation test will be analyzed by either the local laboratory or the central laboratory. A central laboratory will be utilized to test/confirm polyQ status for participation in Cohorts C2 and D2.

PK samples will be analyzed at a laboratory selected by the Sponsor. Duplicate PK samples will be collected in case the original sample is lost, damaged, or not evaluable.

The central laboratory will also receive, track, and ship all blood samples for specialized
genotyping, PK and PD biomarker analysis,
, and CSF samples for PK and PD biomarker analysis, including aliquots from these
samples, retained as backup in case original samples are lost or not evaluable. Residual blood
samples for future DNA testing will be processed to purify DNA and stored by the central
laboratory.
J

15.1.6. Central Facility for Other Assessments

A central facility has been selected by the Sponsor to read and interpret all 12-lead ECGs for this study.

15.2. Study Committees

15.2.1. Safety Surveillance Team

The Sponsor's SST will serve as the study committee. The composition of the SST will follow Sponsor standard operating procedures. The SST, as described in Section 5.3, is responsible for reviewing the safety and PK data prior to dose escalation and at regular intervals in Part 2 and determining whether SAEs and clinically significant AEs result in cohort or study suspension.

16. ADMINISTRATIVE PROCEDURES

16.1. Study Site Initiation

The Investigator must not screen any participants prior to completion of a study site initiation visit. This initiation visit with the Investigator and other site staff, as appropriate, will include a detailed review of the protocol, study procedures, and study responsibilities.

16.2. Quality Control and Quality Assurance

Quality control procedures will be implemented at each stage of data handling to ensure that all data are reliable and have been processed correctly. Data anomalies will be communicated to the sites for clarification and resolution, as appropriate.

During and/or after completion of the study, quality assurance officers named by the Sponsor or the regulatory authorities may wish to perform onsite audits or inspections. The Investigator will be expected to cooperate with any audit or inspection and to provide assistance and documentation (including source data) as requested.

16.3. Monitoring of the Study

The Investigator must permit study-related monitoring by providing direct access to source data and to the participants' medical histories. Source data must be attributable, legible, contemporaneous, original, accurate, and complete. Changes to source data must be traceable, not obscure the original entry, and be explained if necessary (e.g., with an audit trail). The Investigator should maintain a record of the location(s) of essential documents.

The Clinical Monitor will visit the study site at regular intervals during the study and after the study has completed, as appropriate. A clinical site monitoring plan will detail who performs the monitoring, how often, and the extent of review. It also will provide the monitoring strategy, with emphasis on participant safety, data integrity, and critical data and processes.

During these visits, CRFs, supporting documentation, and essential documentation related to the study will be reviewed and any discrepancies or omissions will be resolved. Documentation of results will be provided to the Sponsor or designee in a timely fashion to allow follow-up and verification of compliance with the monitoring plan. Remote evaluation of data (centralized monitoring) may also be conducted and reported as defined in the monitoring plan.

Monitoring visits must be conducted according to the applicable ICH and GCP guidelines to ensure the protection of participant rights and well-being, protocol adherence, quality of data (accurate, complete, and verifiable), study treatment accountability, compliance with regulatory requirements, and continued adequacy of the study site and its facilities.

16.4. Study Funding

Biogen is the Sponsor of the study and is funding the study. All financial details are provided in the separate contracts between the institution, Investigator, and Biogen.

16.5. Publications

Details are included in the clinical study agreement for this study.

16.6. Public Health Emergencies

In the event of a public health emergency that results in site closure, travel restrictions, and/or the study being deprioritized at the site such that clinic visit(s) cannot occur, a protocol deviation would be incurred for any deviation from the protocol-specified visits and assessments, with additional notation that this protocol deviation is due to the public health emergency. If a protocol-specified clinical visit cannot occur because of a public health emergency, the following mitigating options should be pursued (if allowed per local regulations), in order of preference (in which the highest preference option that is feasible should be done): 1) transfer to another active study site that is open, 2) home visit, 3) telemedicine visit (e.g., by telephone or web conference), and 4) local laboratory visit. These mitigating options only apply in the setting of a public health emergency in which a protocol-specified clinic visit cannot occur and should not be pursued solely because of a participant's preference. If the participant does not participate in one of these options, a Safety Telephone call must be conducted within 14 days of the last dosing visit.

A third-party vendor has been engaged to perform assessments at the study participant's home, which may include but are not limited to:

- Limited neurological examination
- Physical examination
- Vital signs
- Height and body weight collection
- •
- •
- •
- C-SSRS
- SVC
- Biological sample collection

A Phase 1/2 MAD Study and Long-Term OLE in Adults With ALS With or Without ATXN2 PolyCAG Expansion

- Pregnancy test (if applicable)
- HHD
- Collection/shipment of ventilation diary records

The following assessments will be performed via telephone (telemedicine) by the site staff:

- ALSFRS-R
- Review of concomitant medications and AEs

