	Screening ¹	Dose 1	тс	Dose 2		Dose 3	тс	Maintenance Dose Visit	тс	CV	тс	Final/ ET Visit	тс	-
Days Assessments ²	-28 to -1	1 (±3)	2 (+1) ³	15	16 (+1) ³	29	30 (+1) ³	57, 85, 113, 141, 169, 197, 225, 253, 281, 309, 337, 365, 393, 421, 449, 477, 505, 533, 561, 589, 617, 645, 673, 701, 729, 757, 785, 813, 841, 869, 897, 925, 953, 981, 1009, 1037, 1065, 1093 (±3)	1 day after each maintenance dose visit	45d after last dose (+/-3)	1 day after Follow- up CV (+1) ³	90d after last dose (+/-3)	1 day after Final/ETV (+1) ³	UV
ICF (Main)	X													
ICF (Informant/ Caregiver)	X													
Confirmation of Eligibility Criteria	X													
Medical History	X	X												
Clinical Laboratory Samples for Viral Serology ⁴	X													
Serum Pregnancy Test ⁵	X													

		Loading Dose Perio	od					Maintenance I	Dose Period	Follov	v Up Peri	od		
	Screening ¹	Dose 1	TC	Dose 2	TC	Dose 3	TC	Maintenance Dose Visit	TC	CV	TC	Final/ ET Visit	TC	
Days Assessments ²	-28 to -1	1 (±3)	2 (+1) ³	15 (±3)	16 (+1) ³	29 (±3)	30 (+1) ³	57, 85, 113, 141, 169, 197, 225, 253, 281, 309, 337, 365, 393, 421, 449, 477, 505, 533, 561, 589, 617, 645, 673, 701, 729, 757, 785, 813, 841, 869, 897, 925, 953, 981, 1009, 1037, 1065, 1093 (±3)	maintenance dose visit (+1) ³	45d after last dose (+/-3)	1 day after Follow- up CV (+1) ³	90d after last dose (+/-3)	1 day after Final/ETV (+1) ³	UV
Urine Pregnancy Test ⁶		X		X		X		X		X		X		
FSH Test ⁷	X													
Physical Examination ⁸	X	X		X		X		X		X		X		X
Neurological Examination (cranial nerves, cerebellar function, motor, and reflexes) ⁹	X	X		X		X		X		Х		Х		X
Weight	X	X						X ¹⁰				X		
Height	X													

225, 253, 281, maintenance dose visit (+1) ³ last dose (+/-3) (17)			Loading Dose Perio	od			Maintenance I	Dose Period	Follov	v Up Peri	od		
(±3) (±3) (±1) (±3) (±3) (±1) (±3) (±3) (±1) (±3) (Screening ¹	Dose 1	TC				тс	CV	тс	ET	TC	-
Vital Signs X X X X X X X X X X X X X X X X X X X		-28 to -1		2 (+1) ³	15 (±3)	29 (±3)	141, 169, 197, 225, 253, 281, 309, 337, 365, 393, 421, 449, 477, 505, 533, 561, 589, 617, 645, 673, 701, 729, 757, 785, 813, 841, 869, 897, 925, 953, 981, 1009, 1037, 1065,	each maintenance dose visit (+1) ³	after last	after Follow-	after last dose	Final/ETV	UV
(temperature, blood pressure, heart rate,	12-Lead ECG ¹¹	X	X		X	X	X		X		X		X
	(temperature, blood pressure, heart rate,	Х	X		X	X	X		X		X		X
Set up study mobile device for Part 2 ¹³			X										

		Loading Dose Perio	d					Maintenance I	Dose Period	Follow	v Up Peri	od		

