The first 2 participants in all cohorts, except cohort C2, will be randomized at a ratio of 1:1 (active drug:placebo) and dosed as a sentinel group. No other participants within the cohort will be dosed until the Investigators have reviewed 72 hours of safety data after dosing the first 2 participants and communicated with the Sponsor Medical Director and Global Medical Safety Physician. Based on this safety evaluation, the Sponsor will determine if the rest of the cohort can be dosed. For the remainder of participants in all cohorts, except for cohort C2, no more than 2 participants will receive their first dose of study treatment on the same day throughout the study. For cohort C2, the participants will be randomized 3:1 (active drug:placebo). Treatment will be staggered by 72 hours for the first 2 participants. The first 2 participants will be dosed as a sentinel group, and no other participant will be dosed until the Investigators have reviewed safety data after dosing the first 2 participants and communicated with the Sponsor Medical Director and Global Medical Safety Physician. This phone call will occur 72 hours after the dosing of the second participant. Based on this safety evaluation, the Sponsor will determine if the rest of the cohort can be dosed. If approved, the third and fourth participants may receive their first dose of study treatment on the same day.

For each participant, a review of all available safety and tolerability data will be performed approximately 7 days after the first dose is administered and before administration of the second dose on Day 15. This single-dose review will be performed by the site's Principal Investigator or

designee and communicated to the Sponsor Medical Director and Global Medical Safety Physician, or their appropriate designees. The Sponsor Medical Director and Safety Physician will determine if each participant can proceed with subsequent doses. The second dose cannot be administered until this review is complete.

Randomization will be performed using IRT. See Figure 1 for a schematic of the study design.

5.1.2. Part 2

Part 2 is an open-label evaluation of BIIB105 administered IT to participants with ALS and polyQ ALS who have completed Part 1 through Week 25 (Day 175 Visit for Cohorts A, B, C1, C2; Day 176 Visit for Cohorts D1, D2).

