5.2. Study Duration for Participants

5.2.1. Study Duration for Participants in Part 1

The total Part 1 study duration for each participant in Cohorts A, B, C1, and C2 will be approximately 29 weeks:

- Screening Period of up to 4 weeks
- Treatment Period of 13 weeks
- Follow-up Period of approximately 12 weeks

Participants in Cohorts A, B, C1, and C2 will have up to 13 CVs and 9 TC during the study, which include at least 1 Screening Visit, 5 Dosing Visits of which the first dose will require an inpatient stay of 2 days, 7 Follow-up Visits, and 9 TC. All visits should be performed within the number of days from the nominal visit day, specified in Section 1. Visit days are calculated with respect to Day 1 (the date of first dose).

The total Part 1 study duration for each participant in D1 and D2 will be between approximately 29 and 41 weeks:

• Screening Period of up to 4 weeks

- Treatment Period of 25 weeks
- Follow-up Period of approximately 12 weeks (only completed if the participant does not enter Part 2 after the Treatment Period)

Participants in Cohorts D1 and D2 will have up to 19 CVs and 15 TCs which will include at least 1 Screening Visit, 8 Dosing Visits of which the first will require an inpatient stay of 2 days, up to 10 Follow-up Visits, and up to 15 TCs.

Participants in Cohorts D1 and D2 who enter Part 2 after their Treatment Period (after the Day 176 Visit) will not be required to complete the follow-up visits in Part 1 that occur after their enrollment in Part 2. Participants from Cohorts D1 and D2 who do not enter Part 2 will have two follow-up clinic visits and two TCs approximately 6 and 12 weeks after their last dosing visit.

Of note, if the Study Sponsor decides to terminate Part 1 without terminating Part 2, participants who are active in Part 1 at the time of the Sponsor's decision will have the opportunity to end Part 1 and screen and enroll into Part 2 prior to completing Week 25.

5.2.2. Study Duration for Participants in Part 2

Study duration for each participant in Part 2 will be up to approximately 172 weeks:

- Screening Period of up to 4 weeks (for participants from Cohorts D1 and D2, Screening Period begins with Day 169 Visit of Part 1)
- Treatment Period of up to approximately 156 weeks: either 104 weeks, OR until the last participant enrolled has had the opportunity for their Part 2 Day 365 visit (Week 52), whichever occurs later
- Follow-up Period of approximately 12 weeks

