For all participants, the Loading Dose Period will be followed by an unblinded Maintenance Dose Period, where participants will receive maintenance doses of BIIB105 administered once every 4 weeks (up to approximately Week 156: either to Week 104, OR until the last participant enrolled has had the opportunity for their Part 2 Day 365 visit [Week 52], whichever occurs later). After the Maintenance Dose Period, participants will have an approximately 12-week follow-up period.

The SST will review safety and PK data from the extension cohorts at regular intervals.

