8.2. Lost to Follow-Up

Participants will be considered lost to follow-up if they repeatedly fail to return for scheduled visits and are unable to be contacted by the study site.

The following actions must be taken if a participant fails to return to the clinic for a required study visit:

• The site must attempt to contact the participant, reschedule the missed visit as soon as possible, counsel the participant on the importance of maintaining the assigned visit

schedule, and ascertain whether the participant wishes to and/or should continue in the study.

- In cases in which the participant is deemed lost to follow-up, the Investigator or designee must make every effort to regain contact with the participant. These contact attempts should be documented in the participant's medical record.
- Should the participant continue to be unreachable, that participant will be considered to have withdrawn from the study with a primary reason of lost to follow-up.

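### The emergency fallback safety call is dated from the last dosing visit, so for a missed follow-up visit its 14-day deadline has normally already passed

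*Protocol*

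**What the plan says.** Section 16.6 of the protocol ranks four alternatives when an emergency prevents a clinic visit: another open site, a home visit, a telemedicine visit, or a local laboratory visit. If the participant takes up none of them, "a Safety Telephone call must be conducted within 14 days of the last dosing visit". The section does not define the last dosing visit and has no separate rule for follow-up visits. Its list of tasks that site staff do by telephone includes "Review of concomitant medications and AEs".

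The visits in question are these:

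- Table 1 (Cohorts A, B, C1, C2): last dose on Day 85, follow-up on Days 130 and 175.
- Table 2 (Cohorts D1, D2): last dose on Day 169, follow-up on Days 214 and 259 for those who do not enter Part 2.
- Table 3 (Part 2): follow-up 45 and 90 days after the last dose. Section 5.3.2 has "maintenance doses of BIIB105 administered once every 4 weeks" before that.

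All these follow-up visits have a window of 3 days either side. Section 5.2.1 uses the same phrase for the end of Part 1 treatment: D1 and D2 participants who do not continue have "two follow-up clinic visits and two TCs approximately 6 and 12 weeks after their last dosing visit".

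The routine call on the day after a lumbar puncture is needed only if the puncture was done (Table 2 footnote 4, Table 3 footnote 3). Table 1 carries no such condition. For any missed visit Section 8.2 says: "The site must attempt to contact the participant, reschedule the missed visit as soon as possible". It sets no date for that contact.

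**The concern.** The event that triggers the call and the event that starts its clock are different. A missed clinic visit of any kind triggers it, but the 14 days run from a dosing visit. During treatment the two are often close together. In follow-up they are weeks apart, so the due date comes before the event that makes the call necessary.

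At stake is how soon adverse events are reviewed in a participant who has stopped dosing and cannot be seen. The call is the last step of the emergency procedure. It should have a date that a site can act on after the visit is lost.

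**Working it through.** This is date arithmetic on the schedules. The only figure in the plan is the 14-day deadline.

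**Spacing of follow-up visits**

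- Table 1: 130 − 85 = 45 and 175 − 85 = 90.
- Table 2: 214 − 169 = 45 and 259 − 169 = 90.
- Table 3 states 45 and 90 directly.

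That makes 2 visits in each of 3 schedules, or 6 schedule slots.

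**Follow-up visits, last dose attended**

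- Nominal days: 45 − 14 = 31 and 90 − 14 = 76 days past the deadline.
- Earliest day in the window: 42 − 14 = 28 and 87 − 14 = 73 days past it.

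**Follow-up visits, final dosing visit missed, clock running from that missed visit**

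- Part 2: the missed visit was due 28 days after the last dose given, so the deadline is 28 + 14 = day 42. That is 45 − 42 = 3 and 90 − 42 = 48 days before the nominal visits. Day 42 is also the first day of the 45-day visit's window. If the missed dosing visit is dated at the end of its own window, the deadline is 28 + 3 + 14 = day 45, the nominal visit day.
- Part 1: a missed Day 85 gives Day 99 (earliest follow-up Day 127), and a missed Day 169 gives Day 183 (earliest follow-up Day 211).

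**Maintenance visits**

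- If the phrase means the last dose given, the deadline is 28 − 14 = 14 days before each nominal visit. In Part 2 this would touch (729 − 57)/28 + 1 = 25 visits to Day 729, or (1093 − 57)/28 + 1 = 38 to Day 1093.
- If it means the missed dosing visit, the site has 14 days after that visit and nothing is wrong.

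**Where the rule works**

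- Part 1 visits 7 days after a dose leave 14 − 7 = 7 days.
- Loading visits are 14 days apart, so on the last-dose reading the deadline falls on the visit day itself. It is already overdue if the visit is abandoned later in its 3-day window.

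**What contact remains after a missed follow-up visit**

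- Cohorts A to C2 keep their calls on Days 131 and 176.
- The other 4 of the 6 slots lose the next-day call, because no lumbar puncture was done.
- Missed Part 2 45-day visit: from the call on day 1 after the dose to the 90-day visit is 90 − 1 = 89 days without a dated contact.
- Missed Day 214: from the Day 177 call to Day 259 is 259 − 177 = 82 days.
- Missed 90-day visit in Part 2, or missed Day 259: no later contact is scheduled.

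**The case against.** The strongest reply is that little depends on this clause. The third alternative is already a telephone or web visit with adverse event review, so the gap reaches only someone who did not use that but would still take a safety call. Section 8.2 requires a contact attempt after any missed visit. Sections 12.3.1 and 12.3.2 have ongoing adverse events and serious adverse events followed until resolved, stabilised or back to baseline, and serious events judged related are reportable after the final visit. All of this stands, and it makes the effect small.

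A second reply is that Section 7.5 already gives a safety call about 24 hours after each procedure, so a deadline counted from the last dose given is arguably met in advance. This is fair against any claim that the site faces an impossible duty. But a call made the day after the dose says nothing about the weeks up to the missed visit, so it does not replace that visit.

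A reader might infer that the fallback fails at every maintenance visit. The documents do not support that. Section 16.6 leaves the phrase undefined. Section 5.2.1 applies it to the end of treatment, which does not settle the maintenance case. Reading it as the missed dosing visit is natural and leaves those visits in order.

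A reader might also infer that events are lost from the primary endpoint, the incidence of adverse and serious adverse events. Nothing in the documents shows this. A late contact can still record an earlier event.

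**Conclusion.** The point holds as a minor drafting fault: a mandatory safety step is dated from the wrong event for follow-up visits. With an attended last dose, the deadline precedes the 45- and 90-day visits by 31 and 76 days in all three schedules. With a missed final Part 2 dose and the clock running from it, the margins shrink to 3 and 48 days at nominal dates, and window use can remove the 3.

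The residual gap is 4 schedule slots: the two Part 2 follow-up visits and D1/D2 Days 214 and 259. These are slots, not expected participants. The documents give no rate at which emergencies prevent visits or at which participants decline all four alternatives. The result rests on nominal dates and on the next-day call lapsing when no lumbar puncture is done.

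**What to change.** In Section 16.6, keep the present deadline wherever it can still be met and add a second one. For example:

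> within 14 days of the last dosing visit; if that date is on or before the day the visit is found not to be possible, the call must be conducted within 14 days of the scheduled date of the missed visit.

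The effects are:

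- A missed Day 8 still needs a call by Day 15. This matters because Section 5.1.1 places the single-dose review "approximately 7 days after the first dose is administered and before administration of the second dose on Day 15".
- A closure known before day 14 still brings a call by day 14. Simply replacing the dose-based date would lose this.
- On the last-dose reading, a Day 15 loading visit lost on or after Day 15 gets a call by 15 + 14 = Day 29.
- After an attended last dose, follow-up visits found impossible on or after day 14 get a call by 45 + 14 = day 59 or 90 + 14 = day 104. For a missed Part 2 45-day visit, the longest stretch without a dated contact falls from 89 to 59 − 1 = 58 days.

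One limit remains: when a closure is known early, the call still comes before the missed visit, and contact afterwards rests on Section 8.2.

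The cost is one clause, with no added visits or staff. Section 14.3 sends every amendment to the ethics committee, and to regulators where local law requires, so the change should travel with another amendment. The SAP for Part 2 and the integrated analysis records that the sponsor ended the study early, so the main use now is in any protocol that reuses this text.
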